10.4.2 Hypothermia treatment

Listing of hypothermia treatment will be provided for the SS. It will include information if subject received hypothermia treatment, age since birth, age since birth when cooling began, target low body temperature, date and time cooling began, date and time cooling ended, duration of cooling (in days, hours and minutes, date and time cooling ended minus date and time cooling started plus 1 minute), timing of cooling in relation to first BRV dose (in hours, relative day and time), date and time rewarming began, date and time rewarming ended, duration of rewarming (in days, hours and minutes, date and time of end of rewarming minus date and time of start of rewarming plus 1 minute) and timing of rewarming in relation to first dose of BRV (in hours, date and time of start of rewarming minus date and time of first BRV dose).

10.4.3 Mother's use of AEDs

A listing of mother's use of AEDs (including BZDs and/or opiates) with the information on mother taking AEDs (BZDs and/or opiates) at the time of delivery, taken medication, dose per intake will be provided for the SS.

10.4.4 Sarnat scale

The Sarnat grading scale comprises 6 components: alertness, muscle tone, seizures, pupils, respiration, and duration assessed together to provide 3 stages (Grade I [mild]; Grade II [moderate]; Grade III [severe]) of HIE. Summaries of shift from Baseline to 24h, 48h, 72h, 96h (72h and 96h visits are for Confirmatory Cohorts only) and last value (defined as the latest available value) will be provided based on the categories Grade I (Mild), Grade II (Moderate) and Grade III (Severe) by individual cohorts and for overall combined Confirmatory Cohorts for the SS subjects with HIE. A listing of Sarnat scale will be provided.

10.4.5 Thompson score

Thompson score ranges from 0 to 22 and is calculated by adding the scores from all 9 aspects of the neurological examination of infants with HIE.

Observed values and changes from Baseline in Thompson score will be summarized for post-baseline visits and time points by individual cohorts and for overall combined Confirmatory Cohorts for the SS subjects with HIE. A listing of Thompson score will be provided for the SS.

10.4.6 N-PASS scale

The N-PASS scale was developed as a clinically relevant tool to assess ongoing or acute pain in neonates and infants, as well as sedation levels. The 5 indicators are: (1) crying/irritability (silent cry observed in the intubated infant is scored as a cry), (2) behavior/state, (3) facial expression, (4) extremities/tone, and (5) vital signs. Points are added to the preterm infant's pain score to approximate the normal response of a full-infant. These points were derived from the Premature Infant Pain Profile pain assessment tool (Stevens et al, 1996). Gestational age groups are <28 weeks (3 points), 28 to 31 weeks (2 points), 32 to 35 weeks (1 point), and >35 weeks (0 points). Scores range from 0 to 13. Behavioral state as a modifier was not included in the development of N-PASS, as it was designed initially for ongoing pain assessment (Hummel et al, 2010).

The N-PASS total Sedation score will be calculated as the sum of negative or zero scores of individual indicators (0, -1, -2), the range of sedation score is from 0 to -10. A score of 0 is given if the infant has no signs of sedation, does not under-react. Deep sedation is when the score is from -10 to -5, light sedation is when the score is from -5 to -2.

The N-PASS total Pain/Agitation score is calculated as the sum of positive scores of individual indicators (1, 2). The total pain score ranges from 0 to 11. Add 1 if gestational age is <30 weeks.

Observed values and changes from Baseline in N-PASS total sedation and total pain scores will be summarized for post-baseline visits and time points by individual cohorts and for overall combined Confirmatory Cohorts for SS subjects.

A listing of N-PASS scores will be provided for the SS.

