6 SELECTION AND WITHDRAWAL OF SUBJECTS

6.1 Inclusion criteria

To be eligible to participate in this study, all of the following criteria must be met:

1. An Independent Ethics Committee (IEC)-approved written ICF is signed and dated by the parent(s) or legal representative(s).
- 2a. Confirmation on VEEG of ≥ 2 minutes of cumulative ENS or ≥ 3 identifiable ENS prior to entering the Evaluation Period (ENS is defined as a seizure lasting for at least 10 seconds on VEEG), despite receiving previous AED treatment for the treatment of electroencephalographic seizures.

The occurrence of ENS during an up to 1-hour period must be confirmed either by the local or central VEEG reader prior to drug administration. Preferably, the central VEEG reader should confirm the required ENS.

3. Subject is male or female and must be at least 34 weeks of CGA. In addition, term neonates up to 27 days of PNA and preterm neonates up to 40 weeks of CGA and 27 days of PNA can be enrolled.
4. Subject weighs at least 2.3kg at the time of enrollment.
5. Subjects with or without concomitant hypothermia treatment.

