11.3.5 N-PASS

The psychometric parameters, including N-PASS, will be measured at the study timepoints as described in [Table 5-1](#) and [Table 5-2](#) for the Exploratory and Confirmatory Cohorts, respectively; and in [Table 5-3](#) during the BRV Extension Period and Safety Follow-Up Period for both the Exploratory and Confirmatory Cohorts.

The N-PASS was developed as a clinically relevant tool to assess ongoing or acute pain in neonates and infants, as well as sedation levels. The 5 indicators are: (1) crying/irritability (silent cry observed in the intubated infant is scored as a cry), (2) behavior/state, (3) facial expression, (4) extremities/tone, and (5) vital signs. Points are added to the preterm infant's pain score to approximate the normal response of a full-term infant. These points were derived from the Premature Infant Pain Profile pain assessment tool (Stevens et al, 1996).

Gestational age groups are <28 weeks (3 points), 28 to 31 weeks (2 points), 32 to 35 weeks (1 point), and >35 weeks (0 points). Scores range from 0 to 13. Behavioral state as a modifier was not included in the development of N-PASS, as it was designed initially for ongoing pain assessment (Hummel et al, 2010).

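### SAP 10.4.6 gives two incompatible preterm corrections for the N-PASS pain/agitation score, and the one in the scoring paragraph adds nothing for any eligible baby

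*SAP*

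**What the plan says.** SAP 10.4.6 describes the instrument in its first paragraph and gives scoring instructions after it.

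The first paragraph lists five items ("The 5 indicators are: (1) crying/irritability (silent cry observed in the intubated infant is scored as a cry), (2) behavior/state, (3) facial expression", then extremities/tone and vital signs) and says that a preterm infant's pain score is raised by gestational age: "Gestational age groups are <28 weeks (3 points), 28 to 31 weeks (2 points), 32 to 35 weeks (1 point), and >35 weeks (0 points"). It closes with "Scores range from 0 to 13". Protocol 11.3.5 has the same tiers and range: "32 to 35 weeks (1 point), and >35 weeks (0 points). Scores range from 0 to 13". It has no other correction.

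The scoring paragraph for pain reads "The N-PASS total Pain/Agitation score is calculated as the sum of positive scores of individual indicators (1, 2") and continues: "The total pain score ranges from 0 to 11. Add 1 if gestational age is <30 weeks". Observed values and changes from Baseline in the sedation and pain totals are then summarized by cohort for the Safety Set, and the scores are listed.

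Protocol 6.1, criterion 3, sets the age limits: "Subject is male or female and must be at least 34 weeks of CGA", and "term neonates up to 27 days of PNA and preterm neonates up to 40 weeks of CGA and 27 days of PNA can be enrolled". SAP 3.3 derives gestational age as corrected gestational age minus postnatal age at enrollment, with postnatal age rounded up to whole weeks. SAP Table 3.1, which lists changes from the protocol's analyses, has no entry on N-PASS.

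**The concern.** A programmer deriving the pain total finds two corrections and two ranges in one SAP section, with nothing to say which governs. The choice matters only for preterm babies, but the protocol expressly admits them and SAP 6.1 reports them as a category. The correction is there to bring a preterm infant's score to the level expected of a term infant. If the scoring paragraph is followed and its threshold lies below the youngest eligible gestational age, that adjustment disappears. At stake are the observed pain/agitation values in the safety tables and listings.

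**Working it through.** **Inputs.** Five items, each scoring at most 2 for pain (SAP 10.4.6). Tiers of 3/2/1/0 points (SAP 10.4.6, protocol 11.3.5). One point below 30 weeks (SAP 10.4.6). Minimum corrected gestational age 34 weeks 0 days = 34 × 7 = 238 days, and maximum postnatal age 27 days (protocol 6.1). Gestational age = corrected gestational age − postnatal age, the latter rounded up to weeks (SAP 3.3).

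**1. The stated ranges.** The item sum is at most 5 × 2 = 10. The tiered rule gives 10 + 3 = 13 and the single-point rule gives 10 + 1 = 11. Each range therefore belongs to its own correction. Applying both would give 10 + 3 + 1 = 14, which matches neither.

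**2. Lowest eligible gestational age.**
- In days: 238 − 27 = 211 = 30 × 7 + 1, or 30 weeks 1 day.
- By SAP 3.3: 27 / 7 = 3.86, rounded up to 4; 34 − 4 = 30 weeks.
- If corrected gestational age were meant: at least 34 weeks.

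None of these is below 30. Enumerating every eligible pair of corrected gestational age and postnatal age, in days and with SAP 3.3 rounding, also finds none below 30. Under the single-point rule the reachable maximum is thus 10, not 11. The 3-point tier (<28 weeks) is out of reach too, so the tiered rule tops out at 10 + 2 = 12.

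**3. Points added for eligible babies**, reading the tiers as completed weeks at birth:

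| Gestational age at birth | Tiered rule | Single-point rule | Difference |
|---|---|---|---|
| 30w1d to 31w6d | 2 | 0 | 2 |
| 32w0d to 35w6d | 1 | 0 | 1 |
| 36w0d or more | 0 | 0 | 0 |

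**4. Who can be in the 2-point row.** A baby born by 31w6d (223 days) reaches 238 days only at 238 − 223 = 15 days of age or later, and must also weigh at least 2.3 kg at enrollment (criterion 4). The documents do not allow a count of such babies.

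**5. Change from Baseline.** With a correction c fixed for the baby, (S_visit + c) − (S_baseline + c) = S_visit − S_baseline, so c cancels. It would not cancel if the tier followed age at each visit. A baby in the 1-point tier at 34 to 35 weeks would drop to 0 points by the Safety Follow-Up Visit, about 30 days after the last dose, which would show as a spurious 1-point fall.

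**The case against.** The best reply is that only one rule is operative. The opening paragraph of SAP 10.4.6 closely follows protocol 11.3.5, speaks of how the scale was developed and cites literature; the instructions on calculating totals come later. That reading is reasonable, but it does not clear the text. The SAP does not label the paragraph as background, and the paragraph itself says that points are added. If it is background, the protocol's scoring has been replaced by a correction that never operates in this population.

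The second reply is about size, and it stands. Protocol 4.3.2 and SAP 2.2.3.2 define the variable as change from Baseline, listed among the other safety variables. SAP 4.5 says that no tests are done. SAP 3.3 takes postnatal age at enrollment, so the derived gestational age is already fixed per baby and the correction cancels. A reader might infer that the defined change variable is biased; on the SAP's own definition of gestational age it is not.

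Third, the silence of Table 3.1 is a weak charge. That table covers changes to analyses, whereas protocol 11.3.5 is an assessment section and the protocol's analysis text asks only for a descriptive summary of the score. A record is needed only if the sponsor keeps the rule that differs from the protocol.

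**Conclusion.** The inconsistency is real and minor. Observed total pain/agitation scores differ between the two rules by 1 point (gestational age 32 to 35 weeks) or 2 points (30 to 31 weeks) on an item sum of at most 10. Change from Baseline with gestational age fixed per baby, the sedation score and babies above 35 weeks are untouched. No efficacy or primary PK result is involved.

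Some stronger readings are tempting but lack support:

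- That the SAP's scores would be too low. They are lower than under the protocol's rule. The documents do not show which N-PASS version the sites score, so neither rule can be called the right one for the data collected.
- That the summaries mix corrections. Nothing in the SAP applies different rules to different babies or visits.
- That the affected group is exactly those born before 36 weeks. SAP 3.3 counts any baby aged 7 days or younger as one week old. Taking corrected gestational age in whole weeks, a baby enrolled in the first week at 36 weeks has a derived gestational age of 36 − 1 = 35 and falls in the 1-point tier, even if born in week 36.
- That the single point could never be given at all. This holds for babies who meet criterion 3. The Safety Set includes every dosed baby, so one enrolled in deviation from that criterion could be below 30 weeks.

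The conclusion rests on the current age criterion and on reading the tiers as completed weeks.

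**What to change.** Before database lock, keep one correction and its matching range in SAP 10.4.6. The default is the protocol's tiered rule with 0 to 13, deleting the sentence on 0 to 11 and the extra point below 30 weeks. First check the eCRF or site scoring form. If it uses the single-point version, delete the tiered text instead and record the departure from protocol 11.3.5 in the SAP.

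In either case state that the correction uses gestational age at birth and stays constant across visits. SAP 3.3 already implies this, but 10.4.6 should say so because N-PASS is repeated at down-titration and Safety Follow-Up.

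The cost is a sentence or two of SAP text and a check of the form. No new data are needed, since the item scores and gestational age already feed planned derivations.

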10.4.7 EEG parameters

A listing of video EEG monitoring (start date and time, stop date and time, was this temporarily stopped, interim stop time, reason for temporary stop, restart time, was EEG permanently discontinued, reason for discontinuation) for the SS and a listing of reactivity to stimulus on vEEG (change of background activity with auditory stimulus, change of background activity with painful stimulus) will be provided for the SS.

10.4.8 Biometric parameters

Biometric parameters are body length, body weight and head circumference. Observed values and changes from Baseline in biometric parameters will be summarized for post-baseline visits and time points by individual cohorts and for overall combined Confirmatory Cohorts for SS subjects. A listing of biometric parameters will be provided for the SS.

10.4.9 Mechanical ventilation

Mechanical ventilation variables:

– Number and percentage of subjects requiring mechanical ventilation during the Evaluation Period [*derivations*: for subjects from the Exploratory Cohort, the numerator is defined as the number of subjects with the mechanical ventilation start date and time after the initial BRV dose and no later than 48 hours after the start date and time of the initial BRV dose. For subjects from the Confirmatory Cohort, the numerator is defined as the number of subjects with the mechanical ventilation start date and time after the initial BRV dose and no later than 96 hours after the start date and time of the initial BRV dose, the denominator is defined as the number of subjects in the FAS].

– Duration of mechanical ventilation during the Evaluation Period [*derivations*: the duration of mechanical ventilation during the Evaluation Period is defined if the start date and time of the ventilation is after the first BRV dose and not later than 48 hours after the first BRV dose for subjects from the Exploratory Cohort and if the start date and time of the mechanical ventilation is after the first BRV dose and no later than 96 hours after the first BRV dose for subjects from the Confirmatory Cohorts. For subjects from the Exploratory Cohort, the duration is calculated as end date and time of the mechanical ventilation minus the start date and time of the ventilation if the end date and time of the ventilation is no later than 48 hours after the first BRV dose for subjects. If the end date and time of the ventilation is later than 48 hours after the first BRV dose, then the duration is calculated as 48 hours minus start date and time of the ventilation. For

subjects from the Confirmatory Cohorts, the duration is calculated as end date and time of the ventilation minus the start date and time of the ventilation if the end date and time of the mechanical ventilation is no later than 96 hours after the first BRV dose. If the end date and time of the ventilation is later than 96 hours after the first BRV dose, then the duration is calculated as 96 hours minus start date and time of the ventilation. The duration is calculated in hours, i.e. the number of days is multiplied by 24, then the number of hours added, and the number of minutes divided by 60 is added].

Summary table will display the number and percentage of subjects requiring mechanical ventilation during the Evaluation Period and descriptive statistics for the duration of mechanical ventilation during the Evaluation Period. The summary table will be presented by individual cohorts and for overall combined Confirmatory Cohorts for SS subjects.

Listing of mechanical ventilation will be provided for the SS.

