11.3.9 Mechanical ventilation

Numbers and percentage of subjects requiring mechanical ventilation will be recorded from Baseline through the 48-hour Evaluation Period for the Exploratory Cohort and the 96-hour Evaluation Period for the Confirmatory Cohort.

Duration of mechanical ventilation will be recorded over the Evaluation Period.

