3.6 Analysis sets

3.6.1 Safety Set

The Safety Set (SS) will consist of all enrolled subjects who take at least 1 dose of BRV. All safety analyses will be performed on the SS for the Exploratory Cohort and the Confirmatory Cohort(s).

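### SAP 10.4.9 counts and times mechanical ventilation only if it starts after the first BRV dose, and its FAS denominator contradicts the Safety Set named for the same table

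*SAP*

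**What the plan says.** Protocol 4.3.2 and SAP 2.2.3.2 list two ventilation variables among the other safety variables: how many babies (count and percentage) need a ventilator in the Evaluation Period, and for how long. Neither section restricts when ventilation began. Protocol 11.3.9 says "Numbers and percentage of subjects requiring mechanical ventilation will be recorded from Baseline through the 48-hour Evaluation Period" in the Exploratory Cohort, and through the 96-hour period in the Confirmatory Cohorts.

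SAP 10.4.9 derives the count more narrowly. For the Exploratory Cohort it is the "number of subjects with the mechanical ventilation start date and time after the initial BRV dose and no later than 48 hours after" that dose. For the Confirmatory Cohorts it is the "number of subjects with the mechanical ventilation start date and time after the initial BRV dose and no later than 96 hours after" it. Duration follows the same rule, tied to that dose: "the duration of mechanical ventilation during the Evaluation Period is defined if the start date and time of the ventilation is after the first BRV". The derivation closes by saying that "the denominator is defined as the number of subjects in the FAS".

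The same section then says of the output: "The summary table will be presented by individual cohorts and for overall combined Confirmatory Cohorts for SS subjects". SAP 3.6.1 is general: "All safety analyses will be performed on the SS for the Exploratory Cohort and the Confirmatory" cohorts. SAP 10 repeats that safety analyses use the SS.

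**The concern.** The variable is named for ventilation needed in the period, but the derivation measures ventilation begun in the period. The difference matters in this population. The documents expect babies with HIE, require at least 2 babies under hypothermia treatment in each cohort, allow prior phenobarbital and midazolam, and list respiratory distress syndrome as an anticipated SAE. Some babies may well be on a ventilator when BRV starts. The summary table would report them as not ventilated and leave their hours out of the duration statistics.

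Separately, a programmer cannot use both the FAS and the SS as the base of one percentage. The FAS is selected on the amount of interpretable EEG, which is unrelated to whether a baby needed ventilation.

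**Working it through.** **1. Numerator.** Protocol 4.3.2 asks for need in the period. Protocol 11.3.9 records from Baseline. Protocol 8.1.1 and 8.2.1.1 list ventilation among the pre-dose assessments. SAP 10.4.9 requires a start after the first dose. A baby ventilated without a break since before that dose adds 0 to the numerator. SAP 3.10, which declares changes to protocol-defined analyses, does not mention this restriction. Version lag does not explain it either: the protocol's ventilation wording dates from Protocol Amendment 3, and the SAP is based on Amendment 6.

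**2. Duration.** With time 0 at first dose and T = 48 h or 96 h, hours ventilated inside the period are min(end, T) − max(start, 0). For an illustrative Confirmatory baby ventilated from 10 h before to 60 h after first dose: min(60, 96) − max(−10, 0) = 60 − 0 = 60 h. Under the SAP this baby has no defined duration.

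**3. What the percentage estimates.** Let N be the babies in the set, B those ventilated continuously since before first dose, and W those starting later.
- SAP rule: W / N
- Prevalence in the period: (B + W) / N
- Incidence among babies at risk: W / (N − B)

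The three agree when B = 0. Once B > 0, the SAP figure is below prevalence. If W > 0 as well, it is also below incidence at risk, because the B babies stay in the denominator but cannot enter the numerator unless they come off and are re-ventilated.

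**4. Size.** The documents state no ventilation rate, so there is no planned figure to reproduce. Assumptions: N = 36 (three Confirmatory Cohorts of 12), FAS = SS, B from 10% to 75% of N, W 10% or 20% of the rest, all rounded to whole babies.

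| B | W | SAP rule W/36 | Prevalence (B+W)/36 | At risk W/(36−B) |
|---|---|---|---|---|
| 4 | 3 | 8.3% | 19.4% | 3/32 = 9.4% |
| 4 | 6 | 16.7% | 27.8% | 6/32 = 18.8% |
| 9 | 3 | 8.3% | 33.3% | 3/27 = 11.1% |
| 9 | 5 | 13.9% | 38.9% | 5/27 = 18.5% |
| 18 | 2 | 5.6% | 55.6% | 2/18 = 11.1% |
| 18 | 4 | 11.1% | 61.1% | 4/18 = 22.2% |
| 27 | 1 | 2.8% | 77.8% | 1/9 = 11.1% |
| 27 | 2 | 5.6% | 80.6% | 2/9 = 22.2% |

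The SAP rule runs from 2.8% to 16.7%; prevalence runs from 19.4% to 80.6%.

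**5. Denominator.** SAP 10.4.9 names the FAS for the percentage and the SS for the table. If the FAS is smaller than the SS, the choice moves the result: with 4 new starts, 4/36 = 11.1% on an SS of 36, but 4/30 = 13.3% or 4/27 = 14.8% on assumed FAS sizes of 30 or 27.

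For the Exploratory Cohort, SAP 3.6.2 requires VEEG data from the Baseline period. The protocol gives a Baseline Period only to the Confirmatory Cohorts, Section 5.1 ties VEEG monitoring to those cohorts, and Table 5–1 has no VEEG row. Few or none of the planned 6 babies would be expected to qualify.

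**The case against.** **Counting only new starts is a legitimate choice.** It parallels the treatment-emergent AE definition in SAP 10.2, and in an uncontrolled study ventilation carried over from before BRV says little about the drug. This stands as a reason to report new starts. It does not rescue the rule as written: the variable is named for need in the period, and a proper incidence would exclude babies already ventilated from the denominator.

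**A reader might infer that already ventilated babies are lost.** The documents do not support that. SAP 10.4.9 also provides an SS listing that would show them, and a baby re-ventilated after BRV would count. The loss is confined to the summary count and the duration statistics.

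**A reader might infer that the Exploratory denominator is zero and the percentage cannot be computed.** That is too strong. No rule restricts the FAS to Confirmatory babies, and SAP 5.1 tabulates FAS numbers by cohort. Protocol 8.1.2 still lists video-EEG for the Exploratory Evaluation Period, without timepoints. The rationale for Protocol Amendment 5 records one baby enrolled before that amendment removed the 2-hour Baseline EEG. The FAS clause can also be read as attached only to the Confirmatory sentence, in which case the general SS rule would supply the Exploratory base. Empty or nearly empty is as far as the text goes.

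**Pre-dose start times may not be captured.** No section shows that intubation times before Baseline are recorded. This is fair, but the repair does not need them.

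**Weight.** These are other safety variables in a descriptive study without statistical tests (SAP 4.5). That limits the consequence but does not make the rule right.

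**Conclusion.** The point holds in two parts, both evident from the text. First, the numerator and duration rules in SAP 10.4.9 do not measure the protocol variable: a baby ventilated continuously since before the first dose is summarised as not ventilated and without duration. Second, the FAS denominator contradicts the SS named for the same table and the SS rule for all safety analyses.

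The direction is certain whenever at least one baby in the set is continuously ventilated since before first dose: the summary understates ventilation in the period. The size is not known. About 3% to 17% against about 19% to 81% is an illustration resting on an assumed 10% to 75% ventilated at first dose, 10% to 20% of the rest starting later, and FAS = SS, so it contains no denominator effect. No single value in that range can be called the true rate. That the Exploratory FAS is likely empty or nearly empty is an inference from the FAS definition and the current schedule. The point should be corrected before analysis; it does not affect the primary PK variable or the efficacy results.

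**What to change.** Amend SAP 10.4.9 as follows.
- Count any subject whose ventilation overlaps the Evaluation Period (48 h Exploratory, 96 h Confirmatory).
- Compute duration from the later of first dose and ventilation start to the earlier of ventilation end and 48 h or 96 h. The end cut-off is already in the section. For episodes begun before the dose, status at first dose replaces the start time, so earlier intubation times are not needed.
- Replace the FAS with the SS, by cohort, as denominator.
- Show two further rows: ventilated at first dose, out of the SS; and newly ventilated, out of those not ventilated at first dose.

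The cost is SAP wording and table programming. Ventilation is already a pre-dose assessment in both cohorts, but the sponsor should confirm that the case report form gives status at first dose and an end time for episodes already under way.
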